6 ETHICS AND REGULATORY COMPLIANCE

6.1 Independent Ethics Committee (IEC) and Competent Authority

In compliance with ICH-GCP, the European Medical Device Directives, the German Medical Device Act and its Ordinance on Clinical Trials with Medical Devices (MPKPV), the study approved by the responsible Ethics Committee in Munich (Ethik-Kommission der Medizinischen Fakultät der Technischen Universität München) on November 14th, 2014, and by the German Federal Institute for Drugs and Medical Devices [Bundesinstitut für Arzneimittel und Medizinprodukte (BfArM)] on December 09th, 2014, and before any potential patient underwent any study-specific procedures.

6.2 Ethical and Legal Conduct of the Study

This investigation was conducted in compliance with the ethical standards having their origin in the Declaration of Helsinki, with ICH-GCP, ISO 14155:2011 and with all relevant German and European laws and regulations governing medical devices and clinical trials on humans.

6.3 Patient Information and Consent

To avoid any possible effect of the study on a patient's decision to undergo necessary Boston keratoprosthesis surgery, only patients who had already been scheduled for surgery with Boston keratoprosthesis implantation were approached about the possibility of participating in the ARGOS-KP01 clinical investigation.

Each potential patient was thoroughly informed about the device and the aims and procedures of the investigation through appropriate EC approved written patient information material and in an individual discussion with an investigator. Information given included the potential risks and benefits associated with the implantation and use of the ARGOS-IO pressure sensor and study participation, as well as the explicit statement that the patient's participation was voluntary and could be ended by the patient at any time. The investigator answered any study-related questions the potential patient may have had. Prior to undergoing any study related procedure all patients signed and dated Patient Informed Consent forms, which were then countersigned and dated by the informing investigator. Patients were given one copy for their own records. The second copy was filed in the Investigational Site File.

Copies of the informed consent form and patient information are included in Annex D.

9 ANNEXES TO THE REPORT

Annexes to the report are provided separately. They include:

Annex A: Clinical Investigation Plan ARGOS-KP01

Reference Number: ARGOS-KP01

Revision B, 03-OCT-2014

A prospective, open-label, monocenter clinical investigation to assess the safety and performance of ARGOS-IO system in patients undergoing implantation of a Boston Keratoprosthesis (BKPro)

Clinical Investigation Plan ARGOS-KP01

Reference Number: ARGOS-KP01

Revision C, 17-MAR-2015

A prospective, open-label, monocenter clinical investigation to assess the safety and performance of ARGOS-IO system in patients undergoing implantation of a Boston Keratoprosthesis (BKPro)

Clinical Investigation Plan ARGOS-KP01

Reference Number: ARGOS-KP01

Revision D, 05-MAY-2015

A prospective, open-label, multicenter clinical investigation to assess the safety and performance of ARGOS-IO system in patients undergoing implantation of a Boston Keratoprosthesis (BKPro)

Clinical Investigation Plan ARGOS-KP01

Reference Number: ARGOS-KP01

Revision E, 29-JAN-2016

A prospective, open-label, multicenter clinical investigation to assess the safety and performance of ARGOS-IO system in patients undergoing implantation of a Boston Keratoprosthesis (BKPro)

Annex B: Investigator's Brochure

Reference Number: ARGOS-KP01

Rev. A, 15-SEP-2014

 Implantata Ophthalmic Products GmbH	Clinical Investigation Report ARGOS-KP01	Revision A Page 114 of 114
--	---	-----------------------------------

Investigator's Brochure

Reference Number: ARGOS-KP01

Rev. B, 29-JAN-2016

Annex C: Instructions for Use

Annex D: Patient Informed Consents

Patienten-Information und –Einwilligung, Version 2.1, 24-FEB-2015

Patienten-Information und –Einwilligung, Version 3.0, 18-SEP-2015

Patienten-Information und –Einwilligung, Version 4.0, 02-FEB-2016

Annex E: Statistical Analysis Plan (SAP)

Statistical Analysis Plan

A prospective, open-label, multicenter clinical investigation to assess the safety and performance of ARGOS-IO system in patients undergoing implantation of a Boston Keratoprosthesis

Reference Number: ARGOS-KP01

Version 1.0, 09-JAN-2018

Annex F: Relevant Data Sets

Final Statistical Output – Listings

Version 2.0 (21FEB2018)

Reference Number: ARGOS-KP01

Final Statistical Output – Tables

Version 2.0 (21FEB2018)

Reference Number: ARGOS-KP01

CRO	Contract research organization
eCRF	Electronic case report form
FSI	First patient in
ICH	International Conference on Harmonization
IMD	Investigational medical device
IOP	Intra-ocular pressure
LSO	Last patient out
MedDRA	Medical Dictionary for Regulatory Activities
N/A	Not applicable
PPS	Per Protocol Set
SAE	Serious adverse event
SAP	Statistical Analysis Plan
SAS	Statistical Analysis System
SFS	Safety Set
SOC	System Organ Class
TFLs	Tables, Figures and Listings
WHO	World Health Organization
WHO-DDE	WHO-Drug dictionary enhanced

Statistical Analysis Plan

Version 1.0 [Final], 09-Jan-2018

1. Introduction

This Statistical Analysis Plan (SAP) is based on the final Protocol for the clinical investigation ARGOS-KP01 and its final eCRF.

Aim of this SAP is to determine prospectively the analysis strategy of this clinical investigation and to describe the methods used for the final analysis. The statistical evaluation of all eCRF parameters as well as other data sources will be performed by the CRO X-act Cologne Clinical Research GmbH (X-ACT) according to this SAP.

This SAP is developed in one step and will be agreed on as final version before the Database Lock.

2. Changes from Protocol including Amendments

- Analysis of Questionnaires and daily IOP self-measurement profiles (patients) will not be performed (not databased)
- Performance analysis will also be done on the Safety Population
- No subgroup analyses will be performed

There are no other changes in the statistical evaluation as compared to the final Clinical Investigation Protocol.

3. Study Overview**3.1. Trial Objective(s)**

The primary objectives of this clinical investigation are:

- Safety: To evaluate the safety and tolerability of the ARGOS-IO pressure sensor in the 12 months following implantation.
- Performance: To evaluate the performance of the ARGOS-IO system compared to manometry in the 12 months following implantation

The secondary objectives of this clinical investigation are:

- Safety: To evaluate the safety and tolerability of the ARGOS-IO pressure sensor use in the first 4, 16 and 28 weeks after implantation.
- Performance: To compare the IOP measured with the ARGOS-IO system to that obtained with manometry at weeks 4, 16 and 28 after implantation.

3.2. Trial Design

The investigation is designed as a prospective, open-label, single-arm, early feasibility study.

The ARGOS-IO system is a non-CE marked investigational medical device composed of the implant and its accessories:

- Implant: ARGOS-IO pressure sensor implant for sulcus placement or trans-scleral fixation
- Accessories: MESOGRAPH reading device, Implant Injector

Concerning patients undergoing implantation of a Boston Keratoprosthesis (BKPro), the ARGOS-IO pressure sensor is intended to be implanted in the human eye in combination with BKPro surgery and to remain in place indefinitely. The ARGOS-IO pressure sensor is intended to be used together with the hand-held MESOGRAPH reading device to telemetrically measure the intraocular pressure (IOP) of patients with a BKPro.

The investigation will consist of 15 visits: the Screening visit, the Surgery visit (Day 0), four early follow-up visits 1, 5, 10, and 15 days after surgery and further nine follow-up visits at weeks 4, 10, 16, 22, 28, 34, 40, 46 and 52.

The Screening visit will be performed within 60 days prior to surgery.

3.2.1. Target Population

Patients undergoing implantation of a keratoprosthetic device to salvage remaining vision

3.2.2. Blinding

This is an open label, non-comparative study with one treatment group. No blinding is requested.

3.2.3. Randomization

This is an open label, non-comparative study with one treatment group. No randomization is performed.

3.3. Trial Conduct

Duration of study:

- Per patient: up to 14.5 months consisting of a Screening period up to 60 days, the implantation of the ARGOS-IO pressure sensor in combination with the BKPro surgery and a follow-up period of 52 weeks
- Scheduled for 25 months from first patient screened to last patient last visit

The trial is conducted at 3 sites located in Germany.

3.4. Trial Variables

3.4.1. Primary Endpoints

Safety:

- Number of patients experiencing a device related SAE at any time during the first 12 months following implantation of the IMD [a]. For the purpose of this analysis, a device-related SAE is defined as any adverse event that both
 - Is considered by the Investigator to have a possible, probable or definite relationship to the device and
 - That leads to any of the following:
 - Death

Statistical Analysis Plan

Version 1.0 [Final], 09-Jan-2018

- A serious deterioration in the health of the patient that results in a life-threatening illness or injury or a permanent impairment of a body structure or function, or that requires medical/surgical intervention to prevent such
- Hospitalization or prolongation of existing hospitalization
- Fetal distress or death or a congenital abnormality or birth defect.

Note: [a] should be read as "following implantation surgery" (in order to allow for situations where implantation was only attempted, see the definition of the Safety Population)

Performance:

- Level of agreement between IOP measurements made using manometry and the ARGOS-IO system over the first 12 months following implantation of the IMD.

3.4.2. Secondary Endpoints**Safety:**

- Incidence, nature, seriousness, severity and duration of adverse events and adverse device events in first 4 weeks immediately following implantation of the ARGOS-IO pressure sensor [a].
- Incidence, nature, seriousness, severity and duration of adverse events and adverse device events in the first 16 weeks following implantation of the ARGOS-IO pressure sensor [a]
- Incidence, nature, seriousness, severity and duration of adverse events and adverse device events in the first 28 weeks following implantation of the ARGOS-IO pressure sensor [a]
- Incidence, nature, seriousness, severity and duration of adverse events and adverse device events in the 12 months following implantation of the ARGOS-IO pressure sensor [a].

Note: [a] should be read as "following implantation surgery" (in order to allow for situations where implantation was only attempted, see the definition of the Safety Population)

Performance:

- Level of agreement between IOP measurements made using surgical manometry and the ARGOS-IO system at 4, 16, 28 and 52 weeks following implantation
- Incidence of device deficiencies in the first 4, 16, 28 and 52 weeks following implantation
- User acceptance of the implantation procedure by means of evaluation of the Implantation Procedure Questionnaire (Investigators)
- User acceptance of the ARGOS-IO system at the investigational site by means of evaluation of the Investigator Acceptance Questionnaire (Investigators)
- Daily IOP self-measurement profiles (patients).

3.4.3. Safety Variables

Safety variables are:

- Occurrence and frequency of adverse events and adverse device effects

3.4.4. Performance Variables

Performance variables are:

- IOP measurements by ARGOS-IO system (at clinic. at home), surgical manometry and finger palpation
- Device deficiencies
- Implantation Procedure Questionnaire (Investigators)
- Investigator Acceptance Questionnaire (Investigators)

3.4.5. Other Variables

Other variables are:

- Informed Consent
- Eligibility assessment
- Demographics (age, sex, ethnicity)
- Medical history (including previous diseases/surgeries) and concomitant diseases
- Prior and concomitant medications and non-drug therapies
- Examination of anterior segment and posterior segment
- Implantation surgery (BKPro, ARGOS-IO)
- IOP measurement by means of Goldmann Applanation Tonometry and pneumotonometry
- Urine pregnancy testing
- Visual acuity
- Perimetry
- End of Clinical Investigation and main reason for early termination.

3.5. Determination of Sample Size

The sample size of 10 to 15 was chosen based on the number of patients undergoing BKPro implantation at the study site in a 12 month period. Although no formal sample size calculation was conducted, this sample size is considered large enough to allow a relatively high probability that common adverse events will be detected and enough data to be collected to estimate the level of agreement of IOP values obtained with ARGOS-IO and surgical manometry.

It is planned to enroll an approximately equal number of patients at each site. Due to the small sample size a stratified design / analysis will not have the power to detect center specific treatment effects.

Patients who drop-out or are withdrawn after implantation will not be replaced.

4. Data Analysis Considerations

4.1. Analysis Populations

All patients screened will be considered for analysis.

Statistical Analysis Plan

Version 1.0 [Final], 09-Jan-2018

The CIP provides the following definitions of analysis populations that will be used for statistical evaluation:

- Safety Population: It comprises all patients for whom ARGOS-IO pressure sensor implantation was attempted, whether or not the implantation was successful.
- Per Protocol Population: It comprises all patients in whom an ARGOS-IO pressure sensor was successfully implanted and for whom the full data set including IOP measurements made in the clinic and safety data according to protocol are available until 28 weeks (Visit 11) after surgery.

Safety analysis will be performed on the safety population. Performance endpoints will be analyzed on the Per-protocol population (primary analysis) and on the safety population.

A definite allocation of patients to the analysis populations is listed in Section 13.2. These patients constitute then the Safety Set (SFS) and the Per Protocol Set (PPS).

4.2. Definition of Subgroups

Subgroups are addressed in the CIP but will not be considered for analysis.

4.3. Analysis Time Points

A schedule of assessments is given in section 8.5 of the CIP.

4.4. Definition of Derived Variables

In case a proportion for a specified criterion is computed, all patients meeting the criterion will be divided by the number of all patients within a population.

In this study, Baseline is the value recorded at Screening visit. If no value at Screening visit is available, the pre-surgical value will be used as Baseline assessment (if applicable).

Changes from Baseline (if applicable) will be computed as follows:

- Absolute change (original unit): post-Baseline value – Baseline value
- Relative change (%): $100 \times (\text{post-Baseline value} - \text{Baseline value}) / \text{Baseline value}$
If the Baseline value is 0, no relative change will be computed.

Adverse events should be documented from the point of surgery until the patient is discharged from the clinical investigation..

A flag variable will be defined indicating for each adverse event the period of the onset:

- up to 4 weeks (Day 0 – Day 28) after surgery
- after 4 weeks up to 16 weeks (Day 29 – Day 112)
- after 16 weeks up to 28 weeks (Day 113 – Day 196)
- after 28 weeks up to 12 months (Day 197 – max(Day 365, Day of study termination))

Statistical Analysis Plan

Version 1.0 [Final], 09-Jan-2018

4.5. Coding Dictionaries

Coding of medical data is performed by the Data Management department of X-ACT. Internationally recognized and accepted dictionaries are used for the coding of medical terms.

- The coding of the previous and concomitant diseases and adverse events is performed using MedDRA version 20.0.
- Prior and concomitant medication and non-drug therapies is coded using the WHO-Drug Dictionary Enhanced (WHO-DDE, version 2012/Q4).

The version of the used dictionary will be indicated in the tables and listings.

4.6. Protocol Deviations

Protocol deviations are identified during monitoring and classified according to the category affected:

- Patient rights/ welfare
- Patient safety
- Integrity of research
- other

Protocol deviations are specified regarding the involvement of deviation.

- Consent process
- Patient eligibility
- AE/ SAE reporting
- Assessments
- Device implantation
- Visit window / missed visit
- Audit finding that requires corrective action
- Other

4.7. General Presentation of Summaries and Analysis

All data as documented will be presented in individual patient data listings (depicting all data obtained in the eCRFs as well as additional external data). Data will be sorted by patient number and visit. Treated patients will be listed first, followed by Screening failures. Where appropriate, the listings will include changes from Baseline.

Descriptive statistics will be computed as follows:

- Continuous variables will be presented using the number of valid cases, arithmetic mean, standard deviation, minimum value, median, maximum value (summary statistics)
- Categorical variables will be presented by the absolute frequency (n) and the relative frequency (%) for each observed modality including missing values as own category if not otherwise specified (frequency tables).

Further specifications regarding the layout of end-of-text tables and listings are given in Appendix 13.5 of this SAP. A list of all statistical tables, figures and listings to be produced can be found in Appendices 13.3 and 13.4. These overviews also indicate the analysis population(s) for which a respective parameter will be evaluated. Any figures/graphics produced must be legible after been copied in black even if the original version is colored.

Raw SAS procedural outputs will not be presented as statistical evaluation is descriptive only.

4.8. Statistical Software

All statistical analyses will be performed by programming using the software SAS® Version 9.3 or higher (STATISTICAL ANALYSIS SYSTEM, SAS Institute, Cary, NC, USA).

5. Statistical/Analytical Issues

5.1. General Considerations

Analysis data sets following internal standards will be programmed which will be used for the generation of tables, figures and listings (TFLs). To meet common quality control requirements, the analysis of the following variables will be double-programmed by a second biostatistician:

- Overview about the frequency and percentage of patients with device related serious adverse events during the first 12 months (primary safety endpoint)
- Level of agreement between IOP measurements made using manometry and the ARGOS-IO system over the first 12 months following implantation (primary performance endpoint)
- Summary of adverse events by system organ class and preferred term during the first 12 months.

The SAS program codes for all other summary tables, listings or graphics will be reviewed by a second biostatistician and the results checked for consistency at least visually. All SAS programs used for the evaluation will be stored in a study-specific directory on the X-ACT file server together with the corresponding 'list' and 'log' files.

All statistical analyses will be performed in a descriptive way. Two-sided 95% confidence intervals (Pearson-Clopper, e.g. Hartung [4]) will be calculated for overall AE rates. Two-sided 95% confidence intervals will be determined for the lower and for the upper limit of agreement regarding the level of agreement between IOP measurements using manometry and the ARGOS-IO system (Zou [5]).

Usually, all patients within a given analysis population will be considered for analysis.

By-visit tabulations will be based on scheduled visits. If data are described by scheduled visit, the analysis will be based upon only those patients who were on study at a given visit.

Correspondingly, the AE rates will be calculated for those patients who enter the period considered.

5.2. Adjustments for Covariates

N/A – Covariates will not be included in the statistical analyses.

5.3. Handling of Dropouts and Missing Data

Patients terminating the trial prematurely due to whatever reason will be evaluated like any patient completing the trial as per protocol, within the analysis sets they qualify for.

Missing data will not be imputed in any way. In general, missing values will be displayed as own category in frequency tables.

Subjects who dropped out during a scheduled visit will be counted for that visit

Statistical Analysis Plan

Version 1.0 [Final], 09-Jan-2018

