5 DISCUSSION

5.1 Limitations of the Study

Several aspects of the study limited its conclusiveness.

1. Only 12 patients were included and only 9 patients finished the study, which is sufficient to detect problematic design features that lead to common adverse events and still limits the number of patients that could potentially be harmed due to unforeseen events. However, with this low number of patients it is unlikely to detect rare negative effects particularly with regard to the different underlying diseases of these patients and different indications for the Boston-Keratoprosthesis implantation.
2. 12 months follow-up for a device intended for permanent implantation are too short to detect any long-term complications or late device deficiencies in patients with Boston Keraprosthetic. Since the device itself is technical identical to the CE approved EYEMATE-IO device, to be placed into the posterior chamber/ciliary sulcus of the eye during cataract surgery and this device performs well for more than several years, no main device related issues are to be expected.
3. Although surgical manometry is the only available method to accurately measure IOP in BKPro patients, it carries problems in the performance and therefore some limitations for the comparability with ARGOS-IO measurements:
 - a. Due to the puncture of the bulbus and following removal of the needle, aqueous humor can be lost which lead to a decrease of the intraocular pressure.
 - b. The quality of the measurements can be strongly influenced by experience of the investigator.

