10.1. Primary Safety Endpoint: Occurrence of Serious Adverse Device Events (SADE)

The number and percentage of patients experiencing a device related SAE at any time during the first 12 months following implantation surgery will be presented in a table. In addition, a 95% confidence interval will be calculated for the percentage of patients with SADE as specified above.

For the purpose of this analysis, a device-related SAE is defined as any serious adverse event that is considered by the Investigator to have a possible, probable or definite relationship to the device.

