10.2. Secondary Safety Endpoints: Incidence and Description of Adverse Events

All adverse events (AEs) including all adverse device effects (ADEs) as recorded in the CRF module 'Adverse Events' will be analyzed.

Initially, an overview will be generated tabulating the number and proportion of patients (and the total number of events) with

- AEs
- Adverse device effects (all adverse events that are considered by the Investigator to have a possible, probable or definite relationship to the medical device)
- AEs related to procedure (all adverse events that are considered by the Investigator to have a possible, probable or definite relationship to the procedure)
- AEs leading to withdrawal of patient
- serious AEs

All adverse events at any time during the first 12 months following implantation surgery will be considered. In addition, 95% confidence intervals will be presented for the percentage of patients with AE(s) considered as specified above.

Corresponding overview tables will be given describing the number and proportion of patients with adverse events as specified above at any time during the first 4 weeks, during the first 16 weeks, and during the first 28 weeks following implantation of the IMD, respectively. In addition, 95% confidence intervals will be presented for the percentage of patients with AE(s) considered as specified above.

All adverse events with onset date during the period will be considered.

- AEs with incomplete onset date will be regarded with an onset date completed by '01' for the day (when the month and the year of the onset date are known)
- AEs with an unknown onset date will be regarded with an onset date identical to the date of awareness of the AE

Note that AEs will be counted for each period since onset. Reported frequencies are cumulative over the time for this reason.

Adverse events are coded according to the MedDRA terminology. The following summaries will be provided for adverse events broken down by System Organ Class (SOC) and Preferred Term within SOC:

- All AEs
- All AEs by severity (categories: mild, moderate, severe)
- All AEs by causal relationship to IMD (categories: none, unlikely, possible, probable or definite)
- All adverse device effects (all adverse events that are considered by the Investigator to have a possible, probable or definite causal relationship to the device)

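### Patients who leave early without a recorded SADE stay in the 12-month denominator as non-events, so the primary safety percentage can understate risk; no planned analysis uses follow-up time

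*SAP*

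**What the plan says.** SAP 10.1 defines the primary safety output: "The number and percentage of patients experiencing a device related SAE at any time during the first 12 months following implantation surgery", with a 95% confidence interval. SAP 5.1 names Clopper-Pearson as the interval for AE rates.

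The rules that fix numerator and denominator are spread over several sections:

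- SAP 4.4, denominator: "all patients meeting the criterion will be divided by the number of all patients within a population". The same section ends AE documentation when the patient is discharged from the investigation.
- SAP 5.3, early leavers: "Patients terminating the trial prematurely due to whatever reason will be evaluated like any patient completing the trial as per protocol", within the analysis sets for which they qualify. It adds: "Missing data will not be imputed in any way".
- SAP 5.1, AE denominators: "the AE rates will be calculated for those patients who enter the period considered".
- SAP 10.2, periods counted from surgery: "Reported frequencies are cumulative over the time for this reason".

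Neither document plans a time-to-event, exposure-adjusted or sensitivity analysis for early leavers. On completion, Protocol 5.1 (Limitations of the Study) states: "Only 12 patients were included and only 9 patients finished the study".

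**The concern.** The endpoint is a risk over 12 months, but AE recording stops when a patient leaves. Unobserved time can only hide a first SADE; it cannot add one. Counting SADE-free leavers as full-year non-events therefore moves the percentage, if at all, in the favourable direction. The exact interval covers sampling error in x/13 and makes no allowance for missing follow-up.

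The unobserved months were not free of device effects. Protocol Table 11 gives cumulative adverse device effects (ADEs) of 3, 8, 11 and 15 at 4, 16 and 28 weeks and 12 months, so 15 − 11 = 4 of the 15 events began after week 28. They are not all shown to be serious.

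**Working it through.** **1. Denominator in use.** The SADE table is not in the supplied text. The closest visible figures are the any-SOC patient counts in Protocol Table 11: 1/13 = 7.7%, 3/13 = 23.1%, 4/13 = 30.8% and 4/13 = 30.8% at 4, 16 and 28 weeks and 12 months. All reproduce with N = 13, so the denominator does not shrink as patients leave. The sentence in SAP 5.1 about patients entering a period does not change this: the periods are cumulative, so every Safety Set patient enters the 12-month period on Day 0.

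**2. Inputs.**
- Patients with a SADE, x: 1 to 4. The Protocol Summary reports 15 device-related AEs in four patients, six of them serious.
- Leavers, L: 13 − 9 = 4 on the Safety Set, or 12 − 9 = 3 on patients included. The visible text does not account for the thirteenth patient's follow-up.
- Leaving times, and whether leavers had already had a SADE: not shown. The main case below assumes L = 4, all SADE-free.

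**3. Crude rate and bounds.** Crude = x/13 with Clopper-Pearson limits. The largest possible Kaplan-Meier value is x/9, reached if all four left before the first SADE. Worst case = (x + 4)/13.

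| x | Crude x/13 | Exact 95% CI | x/9 | (x + 4)/13 |
|---|---|---|---|---|
| 1 | 7.7% | 0.2 to 36.0% | 11.1% | 38.5% |
| 2 | 15.4% | 1.9 to 45.4% | 22.2% | 46.2% |
| 3 | 23.1% | 5.0 to 53.8% | 33.3% | 53.8% |
| 4 | 30.8% | 9.1 to 61.4% | 44.4% | 61.5% |

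With L = 3, the largest Kaplan-Meier value is x/10 (10.0% to 40.0%) and the worst case is (x + 3)/13 (30.8% to 53.8%).

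**4. Kaplan-Meier for x = 4.** Assumed censoring is either spread (days 73, 146, 219, 292) or early (days 30, 60, 90, 120).

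- *Table 11 timing*: one patient by week 4, two more by week 16, one more by week 28. With events at interval midpoints (days 14, 70, 70, 154):
  - spread: S = (12/13)(11/12)(10/11)(7/8) = 0.673, risk 32.7%
  - early: S = (12/13)(9/10)(8/9)(5/6) = 0.615, risk 38.5%
  - averaged over event times uniform within each interval: about 33% and 38%. With three leavers spread over the year, about 32%.
- *Events uniform over the year*: about 38% (spread) and 42% (early).

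Table 11 gives ADE timing, used here as a stand-in for SADE timing; a first SADE can come later than a first ADE. Its any-SOC counts at 4 and 16 weeks (1 and 3) are also below its Eye Disorders counts (2 and 4), so those rows need reconciling.

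**5. Expected size.** Suppose a constant hazard, leaving unrelated to risk, true 12-month risk p, and four of 13 leaving at time t (fraction of a year). The expected crude rate is {9p + 4[1 − (1 − p)^t]}/13. For p = 20% this is 14.4% if they leave at week 4 and 18.7% at week 40. For p from 10% to 30%, the crude rate averages about 72% (week 4) to 93–94% (week 40) of the true risk.

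**The case against.** The strongest reply is that the effect is unproven and small beside the uncertainty already reported. Every Kaplan-Meier value above lies inside the matching exact interval, and early censoring at days 30 to 120 has no support in the documents. The worst case is a bound, not evidence of bias. The study is descriptive: SAP 5.6 plans no tests, and SAP 3.5 has no formal sample size calculation. SAP 6.1 already plans disposition with reasons for early termination, and SAP 13.4 lists AEs by patient, so with 13 patients a reader could trace each leaver. Kaplan-Meier adds an assumption of non-informative leaving that cannot be checked with so few events. All of this stands, and it makes the point one for sensitivity analysis. It does not supply the missing estimate: listings leave the reader to build it.

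Three stronger readings are tempting, and the documents do not support them.

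- *That all early leavers count as event-free.* A leaver with a recorded SADE counts as an event. The sentence in SAP 5.3 concerns inclusion in analysis sets; the effect arises only when it is combined with SAP 4.4, 10.1 and 10.2.
- *That the result is in fact biased downwards.* The number of leavers (3 or 4), their leaving times and their SADE status are not shown. The bias is zero if they had their SADE before leaving or would have had none.
- *That the safety conclusion rests on this percentage.* The visible conclusions (Protocol 4.8.1, 5.2 and 5.5) compare complications with published experience. None cites the SADE percentage or its upper limit.

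**Conclusion.** The point holds as a limitation of the planned estimate. SADE-free leavers stay as non-events in a 12-month percentage, the possible error runs one way only, and nothing planned shows its size. For x = 4 and four SADE-free leavers, Kaplan-Meier exceeds the crude 30.8% by about 2 to 7 points with Table 11 timing, or about 7 to 12 points with uniform events. The worst case sits at or just above the exact upper limit for x = 3 and x = 4 and above it for x = 1 and x = 2, so the planned interval cannot be taken to cover missing follow-up. These figures depend on the assumed number, timing and SADE status of leavers. This is an inexpensive improvement to a descriptive analysis.

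**What to change.** In SAP 10.1, keep x/13 with its exact interval as the primary result. Add one sensitivity table with:

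1. The Kaplan-Meier 12-month cumulative incidence of first SADE, with its confidence interval, censored at study termination and with non-informative leaving stated as an assumption.
2. The number of SADE-free patients followed to 12 months. Define this by completion of the Week 52 visit: its window is ±7 days around Day 364, so a strict Day 365 cut-off would class some completers as leavers.
3. A worst-case bound counting every SADE-free leaver as an event.

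The dates needed are already used in the SAP: AE onset in 10.2 and study termination in 6.1. The cost is one small table, a Kaplan-Meier estimate that is imprecise with so few events, and possibly a less favourable figure beside the primary one.
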